This study occurs within the Northwestern Medicine health care system.

PRÉCIS

Study Title

Behavioral Economic Applications to Geriatrics Leveraging Electronic Health Records (BEAGLE)

Objectives

The main intent of this study is to determine whether an intervention comprised of 3 electronic health record (EHR) nudges designed using behavioral economic concepts reduces rates of over-prescribing in 3 clinical areas: prostate screenings, urinary testing for non-specific reasons female patients, and treatment for diabetes mellitus (DM). Our primary hypothesis is that practices randomized to receive these nudges will have lower over-prescribing rates in these 3 domains compared to control practices.

Design and Outcomes

We will conduct a multi-site cluster randomized trial of a behavioral intervention targeting overuse of prostate screening, urinary testing, and treatment for diabetes in geriatric patients, with practice as the unit of randomization.

The 3 co-primary outcomes are measured at the patient level, and capture whether an eligible patient received unnecessary treatment for a particular measure. We will report marginal monthly rates of each outcome. These include:

1. Ordering of prostate specific antigen (PSA) for prostate cancer screening in adult men aged 76 years and older
2. Ordering of urinalysis or urine cultures (UA/UC) for non-specific reasons to identify bacteriuria in women aged 65 years and older
3. Overtreatment of diabetes (DM) with insulin or oral hypoglycemic drugs in adults aged 75 years and older.

In the main analysis, we will compare a 12-month historical period to an 18-month intervention period. In subsequent secondary analyses to determine persistence of study effects, we will track all 3 co-primary outcomes for another 12 months after the intervention ceases.

Interventions and Duration

We will randomize clinics to either a brief education arm (clinicians at those clinics receive an invitation to an online education module) or brief education plus 18 months of clinical decision support within the EHR for the three clinical topics above.

The intervention period will be 18 months long, followed by an additional 12 months of data collection to assess persistence of study effects. We will also use data from a 12 month historical baseline period immediately prior to the start of the intervention period.

Sample Size and Population

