10.2 Sample Size and Randomization

Power Calculations

Study power for BEAGLE was designed around estimating minimum detectable absolute rate reductions for the three co-primary outcome measures at the individual level. Power calculations were done for a 2-level mixed effects logistic regression model that included a random intercept for clinic using PASS software. Historic data, from a period spanning X, 2017 – Y, 2018 were used to estimate an inter-clinic correlation coefficient of 0.017. In all calculations, we assumed a two-sided type I error of 5% (Bonferroni-corrected to $0.05/3 = 0.017$), 80% power, 30 clinics in each arm, and that patients would be divided equally between clinics in 2 groups. Initial calculations assumed baseline event rates and sample sizes described in Table 1. These analyses should have been conservative, as our assumed sample size was derived from an historic 12-month period, while the study follow-up period was 18 months. We did not assume any clinic drop-out, as all data will be available via the EHR. With these assumptions, we anticipated having adequate power to detect an absolute difference of roughly 4% for each of the measures. For the PSA and UA/UC outcomes, this corresponded to a relative risk between 0.80 and 0.87; for the DM outcome, it corresponded to a relative risk between 0.73 and 0.81.

Table 1. Summary of power calculations for the BEAGLE study.

	PSA N=9,500			DM N = 6,600			UA/UC N = 15,000		
	20%	25%	30%	15%	20%	25%	20%	25%	30%
Baseline event rate	20%	25%	30%	15%	20%	25%	20%	25%	30%
Minimum detectable absolute rate reduction	4.1%	4.5%	4.8%	3.9%	4.4%	4.8%	3.8%	4.2%	4.4%
Corresponding relative risk	0.80	0.82	0.84	0.74	0.78	0.81	0.81	0.83	0.85

Treatment Assignment Procedures – Constrained Randomization

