10.5 Statistical Analyses

We will use the following descriptive statistics to characterize the sample: Means and medians for continuous measures, frequencies for count data, standard deviations and interquartile ranges for variance.

To test our 3 co-primary hypotheses, we will employ a mixed-effects hierarchical logistic regression model to estimate the adjusted marginal effect over time of each intervention on the 3 co-primary outcomes. Fixed effects will include intervention assignment, time period (historical baseline versus intervention period), time period interacted with intervention assignment, time (continuous, linear), and a 3-way interaction term between time period, intervention, and time (continuous). The coefficient on the 3-way interaction term will represent whether the log-odds of the monthly rate of change in each co-primary outcome differs between intervention and control patients during the intervention period. Providers will be included as random effects. To isolate the effect of the intervention on the co-primary outcomes, we will also include fixed effects for the variables included in the constrained randomization procedure.

The secondary and safety outcomes will be examined in a similar fashion. If they are sufficiently rare (for example, no events in a given month), model convergence may become an issue. First, we plan to expand the time frame from months to quarters and fit the same model. If that fails, we will abandon the time-varying aspect of the analysis and do one pull for the historical baseline period and one pull for the intervention period. The mixed effects logistic regression model would then be run without including continuous time. If that still fails to converge, we will exclude the random effects for providers and use a fixed effects logistic regression model.

Last, the three co-primary outcomes of interest will be examined in the following pre-specified subgroups:

- Sex (DM measures only)
- Race and ethnicity
- Age groups (for UA/UC: 65-74, 75-84, 85+) (for PSA: 76-79, 80-84, 85+) (for DM: 75-79, 80-84, 85+). We will also examine for effects on patients younger than the target populations (for UA/UC: 50-64, PSA: 70-75, DM 65-74).

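### The stated 80% power is for a difference in rate between arms, but the only coefficient Section 10.5 interprets is a difference in monthly slope, for which no power is given

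*Combined protocol and SAP*

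**What the plan says.** Section 10.2 designs the study around "minimum detectable absolute rate reductions for the three co-primary outcome measures at the individual level". It adds: "Power calculations were done for a 2-level mixed effects logistic regression model that included a random intercept for clinic using PASS software". The stated inputs are a two-sided 5% error divided by three, "80% power, 30 clinics in each arm, and that patients would be divided equally between clinics in 2 groups", and an inter-clinic correlation of 0.017. No time, period or interaction term is mentioned.

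Section 10.5 tests the three co-primary hypotheses with a mixed logistic model containing arm, period, period-by-arm, linear time and period-by-arm-by-time. It interprets one of these: "The coefficient on the 3-way interaction term will represent whether the log-odds of the monthly rate of change in each co-primary outcome differs" between arms during the intervention period.

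The hypothesis is worded in two ways. The Précis says that "practices randomized to receive these nudges will have lower over-prescribing rates in these 3 domains compared to control practices", which is a statement about level. Section 10.1 speaks of decreases over time, evaluated through interactions of assignment with time in a difference-in-differences framework. Sections 6.1 and 10.4.1 make each monthly value a 365-day look-back.

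**The concern.** A power statement tells the reader how likely the planned test is to detect a given effect. Here it concerns a gap between two proportions, while the coefficient singled out for interpretation is a difference in rate of change on the log-odds scale. The two have different standard errors and answer different questions. No section gives a detectable slope, an assumed time course or a power for the slope.

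The time course matters. For PSA and urine tests the alert fires at the point of ordering (Section 5.1), so an early drop that then holds is plausible. A slope does not measure the size of such a drop. In addition, both the period-by-arm term and the three-way term could later be presented as the result, for each of three outcomes.

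**Working it through.** **1. What Table 1 powers.** Inputs from Section 10.2: N = 9,500 (PSA), 6,600 (DM) and 15,000 (UA/UC); 60 clinics; two-sided alpha 0.05/3, so z = 2.394. With m = N/60:

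- design effect DE = 1 + (m − 1) × ICC
- effective n per arm = (N/2)/DE
- power = Φ[(d − z × SE0)/SE1], with SE0 pooled and SE1 unpooled

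PSA, 20% falling by 4.1 points, ICC 0.010: m = 158.3, DE = 2.573, n = 1,846, SE0 = 0.01263, SE1 = 0.01261. Power = Φ[(0.041 − 0.03024)/0.01261] = Φ(0.85) = 80%.

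At ICC 0.010 all nine cells give 79.6% to 81.2%. At the stated ICC of 0.017 they give 59% to 65%, and the detectable differences become 4.84/5.30/5.66 (PSA), 4.49/5.10/5.59 (DM) and 4.61/5.04/5.38 (UA/UC) points. The ICC discrepancy is a separate matter. What counts here is that a plain two-proportion cluster formula reproduces the table, so Table 1 is a calculation for a level.

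**2. How an immediate effect looks under the look-back.** Section 5.3's example shows a December 2020 value holding three intervention months out of twelve. After k completed intervention months, an immediate constant effect of size 1 therefore appears as min(k, 12)/12.

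- Mean over k = 1 to 18: (78/12 + 6)/18 = 12.5/18 = 0.694.
- Slope: Σkv = 650/12 + 93 = 147.17. Subtracting 9.5 × 12.5 = 118.75 leaves 28.42. Dividing by 18 × (18² − 1)/12 = 484.5 gives 0.0587 per month.
- Value at time zero (intervention start): 0.694 − 9.5 × 0.0587 = 0.137.

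Fitting the Section 10.5 fixed effects on a linear scale, with 12 baseline and 18 intervention months and no noise, returns the same values:

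| Pattern in the measured value | Three-way term | Period-by-arm term |
|---|---|---|
| Immediate drop, no look-back | 0 | 1.00 |
| Immediate drop, 365-day look-back | 0.059 | 0.137 |
| Linear growth to full size at month 18 | 0.056 | 0 |

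Through the look-back, an immediate drop and a steadily growing effect give almost the same slope. In the second row, neither coefficient is the reduction that Table 1 powers.

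**3. Illustrative power of the three-way term.** Method: analytic variance in a clinic-by-month linear version of the Section 10.5 model, 30 equal clinics per arm, alpha 0.0167, and the effect in the lowest-baseline column of Table 1 (PSA 4.1, DM 3.9, UA/UC 3.8 points). Each range runs from an assumed between-year clinic correlation of 1.0 to 0.8. The documents do not give this correlation.

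| Scenario | PSA | DM | UA/UC |
|---|---|---|---|
| Non-overlapping months, immediate drop | 0.8% | 0.8% | 0.8% |
| Non-overlapping months, linear decline | 34–21% | 26–18% | 46–24% |
| Look-back, immediate drop | 83–62% | 72–55% | 93–68% |
| Look-back, linear decline in practice | 51–33% | 40–29% | 66–37% |

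The 0.8% is alpha/2: the slope is zero, so only chance rejections in the favourable direction count. The first two rows do not use the planned measure and are shown only for contrast. Section 10.5 lists no arm-by-time or period-by-time term. Adding both brings power to about 4–27% in every scenario except the first row.

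**The case against.** The strongest reply is that the plan does not label the three-way term as the sole primary test. The period-by-arm term is in the same model, Section 10.5 aims at an adjusted marginal effect, Section 10.1 calls the framework difference-in-differences, and the Précis promises marginal monthly rates. A slope also fits Section 10.1's wording. All of this stands. It means that no contrast has been named as primary; it does not supply power for the coefficient that is interpreted.

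Three stronger readings are tempting, and the documents do not support them.

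- *A nudge that works at once leaves the slope flat and will be missed.* That holds for non-overlapping monthly data. The plan uses a 365-day look-back, under which the same effect gives a slope of 0.059 per month, slightly more than the 0.056 for linear growth.
- *The trial is underpowered.* With the look-back, the model as listed and an immediate drop, illustrative slope power is 55–93%, which can exceed that of the level test.
- *A slope is the wrong choice.* Section 10.1 allows it. The fault is that the two wordings of the hypothesis and the power statement do not agree.

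A simple switch to the level is not enough either. The raw period-by-arm coefficient depends on where time is set to zero, and an 18-month average of the look-back measure carries only 0.694 of an immediate effect. Taking Table 1 at face value, that average would have power Φ[(2.394 + 0.842) × 0.694 − 2.394] = Φ(−0.15), about 44%, before any gain from baseline adjustment.

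**Conclusion.** The mismatch is real. Section 10.2's 80% and its roughly 4-point difference describe a contrast in level; Section 10.5 interprets a contrast in slope; and no section gives power for the slope. Illustrative slope power runs from about 1% to 93% across all the assumptions tried, and from 29% to 93% under the look-back with the model as listed. The supportable conclusion is that power for this test is unstated and depends on assumptions, not that it is low.

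The fitted coefficients (0.059, 0.137, 0.694) rest on a linear scale, equal months and a window that fills by one twelfth a month. The power figures further assume equal clinics, independent monthly sampling and correct standard errors. They fit DM least well, because that measure uses the latest A1C and the active medication list. They are also approximate for UA/UC, where only the first testing episode in a window counts. The mismatch itself rests on none of these assumptions.

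**What to change.** Name one primary contrast per outcome and use one wording of the hypothesis in the Précis and Section 10.1.

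- **Preferred:** a model-based marginal difference-in-differences in rates, evaluated where the look-back holds only intervention-period data, such as the month-18 value or the average over months 12 to 18, counting completed intervention months. The month-18 value is a single 12-month window, as is the N behind Table 1. Make the three-way slope secondary. Confirm power for this contrast by simulation, since Table 1 includes no baseline comparison and does not follow from the stated ICC.
- **If the slope stays primary:** remove the 80% statement for it and give simulated power with a stated effect trajectory, look-back overlap and correlation structure. State whether clinic is a random effect (Section 10.1 includes it; Section 10.5 lists providers only) and whether the two missing two-way time terms are intended.

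The cost is SAP wording and a short simulation, with no new data or patients. The downside is that the resulting power may be less favourable than 80%.

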10. STATISTICAL CONSIDERATIONS

10.1 General Design Overview

Hypotheses

Our primary hypothesis is that practices randomized to receive behavioral economic interventions will have decreases over time in the over-screening, over-treatment, and over-testing of older patients who

may no longer warrant such care. This hypothesis will be evaluated in an intention-to-treat difference-in-differences framework using a mixed-effects logistic regression model. Fixed effects will include the effects of interventions over time (i.e., interactions between randomization assignment and time), using a historical period 12 months prior to the intervention period. Providers and randomization unit (clinic) will be modeled as random effects.

Design

We will conduct a cluster randomized trial using data abstracted from the EHR at one academic health system. We chose a cluster-randomized design at the clinic level to minimize spillover effects – contamination that might occur if individual providers in close proximity are randomized to different interventions. The study design for BEAGLE included the implementation of a modified constrained randomization scheme, to ensure that clinics in each study arm were similar prior to activation of the intervention.

Outcome measures

This study has 3 co-primary outcomes, referred to as PSA, UA/UC, and DM (defined in Section 6 above, and further detailed in Section 10.4 below). They capture the over-testing, over-screening, and over-treatment of older patients, whose medical needs may have evolved to require less care.

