We used the methodology presented in [cite] to implement the constrained randomization algorithm. First, the study biostatistician ([name]) generated possible 1:1 randomization schemes. Since there were infinitely many ways to randomize the 60 practices into 2 groups, the study biostatistician decided to create 100,000 possible sequences. Second, the balance of the eight prespecified variables (which were “constrained” upon) was then evaluated in the 100,000 possibilities. Schemes were deemed candidate schemes if they had “adequate balance” – that is, the measure of imbalance for each variable (separately) could not surpass a pre-specified threshold. For categorical variables, we allowed no more than a difference of two practices across each arm. For continuous variables, we compared sample means across study arm, and adapted the ideas of the minimal sufficient balance approach. We called a variable ‘adequately balanced’ if a T-statistic from an independent two sample t-test with equal variance was between -0.385 and 0.385, corresponding to a p-value for the individual variable of 0.30. Last, the final sequence was selected from the candidate schemes (which were adequately balanced) at random with equal probability.

As was disclosed in the study protocol paper, we achieved adequate balance for seven of the eight pre-specified variables used in the constrained randomization algorithm. Due to a coding error, we applied balancing criteria for the PSA measure on the number of eligible patients (denominator) and the number of PSA orders (numerator) rather than the annual PSA overtesting rate (#4 above). This is an absolute measure instead of a relative measure that accounts for the size of the eligible patient population at each clinic. For a complete discussion of the implications of this error, please reference the protocol paper.

The study biostatistician ([name]) generated the final randomization in R version 3.6.4 (R Core Team, 2020). [25] Randomization occurred in June 2020. The allocation of the sequence was concealed until

after the intervention period began in September 2020 (due to interruption of regular care during the COVID-19 pandemic).

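### The randomization variables enter the 10.5 model only as time-constant main effects, so they contribute essentially nothing to the intervention-effect terms and do not adjust for change that depends on a clinic's baseline rate

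*Combined protocol and SAP*

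**What the plan says.** Section 10.1 sets the primary test in an "intention-to-treat difference-in-differences framework using a mixed-effects logistic regression model". Section 10.5 lists the fixed effects as assignment, period, "time period interacted with intervention assignment, time (continuous, linear), and a 3-way interaction term between time period, intervention, and time (continuous"). It then reads the effect from the last of these: "The coefficient on the 3-way interaction term will represent whether the log-odds of the monthly rate of change" differs between arms.

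The covariates are introduced with a stated purpose, "To isolate the effect of the intervention on the co-primary outcomes", and the text continues "we will also include fixed effects for the variables included in the constrained randomization procedure". No product of these variables with period or time is listed, so main effects are the natural reading.

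Section 10.2 lists eight clinic-level variables, among them the annual PSA, UA/UC and DM rates. The eligible-patient counts are dated March 2019 to February 2020, and six acquired practices supplied only nine of those months. The same section reports that a coding error applied the PSA balancing criteria to the eligible count and the order count "rather than the annual PSA overtesting rate (#4 above"). It refers the reader to the protocol paper for the implications.

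On random effects, 10.5 says "Providers will be included as random effects", while 10.1 says "Providers and randomization unit (clinic) will be modeled as random effects". The point below holds under either.

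**The concern.** A covariate that is constant within a clinic raises or lowers that clinic's fitted level equally in the historical and intervention periods. The effect terms are contrasts between those periods, or slopes within the second, so the covariate has almost nothing to say about them. The baseline rate is moreover a summary of historical outcomes that are themselves response rows.

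What stays unadjusted is change that depends on where a clinic started. If one arm begins higher by chance, part of that excess tends to fade without any intervention effect, and the arm-by-period or slope term picks this up. Precision that the baseline rate could have supplied is also lost. A reader who sees the covariates listed may take the estimates as adjusted for baseline rate when, in effect, they are not.

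PSA deserves particular care. Its rate was not itself constrained, and taken literally the wording about variables in the procedure could bring in the number of PSA orders instead of the rate.

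**Working it through.** The plan gives no figure for this adjustment. Table 1 rests on a two-level model without a baseline covariate, so there is nothing of the plan's to reproduce on this point.

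**1. Does the main effect move the effect terms?** The 10.5 model was simulated with 60 clinics, 350 providers and 12 + 18 months (from the plan). Assumed: 27 patients per provider-month, provider SD 0.5 and clinic SD 0.24 on the logit scale, a baseline arm difference of 0.6 clinic SD, independent months, 12 replicates per scenario. Largest change in arm × period and in arm × period × time from adding the clinic baseline rate as a main effect:

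- linear model, balanced: about 1e-16 (exact cancellation)
- mixed logistic, balanced: 0.00007 and 0.00003 log-odds
- mixed logistic with provider turnover and six late clinics: 0.0015 and 0.0012
- mixed logistic with a strong arm-specific shift in panel size: up to 0.005 and 0.001

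The between-replicate SD was about 0.02 to 0.035. In the balanced mixed model the covariate did change the arm main effect (0.162 to 0.007) and the provider SD (0.549 to 0.454), but neither is the intervention effect.

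**2. Would an interaction do the job?** With an assumed drift of -0.10 log-odds per clinic SD of baseline and no true effect, mean arm × period in the balanced mixed model was -0.073 without the covariate, -0.073 with the main effect and -0.036 with rate × period and rate × period × time. The same data without drift gave about -0.012. The three-way term was 0.010 in all three fits, because months were independent and the drift was a step.

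**3. Level contrast if the two periods were independent samples.** Inputs: m = N/60 from Table 1, i.e. 9,500/60 = 158 (PSA), 6,600/60 = 110 (DM), 15,000/60 = 250 (UA/UC); ICC 0.017 (section 10.2) and, as an assumed lower value, 0.010; clinic autocorrelation (CAC) 0.7 to 0.9, assumed. Then r = CAC × m × ICC / (1 + (m - 1) × ICC). Change-score variance is proportional to 2(1 - r) and baseline-adjusted variance to 1 - r², so their ratio is 2/(1 + r).

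- Smallest loss (UA/UC, ICC 0.017, CAC 0.9): r = 0.9 × 4.25/5.233 = 0.731; 2/1.731 = 1.155, about 16%.
- Largest loss (DM, ICC 0.010, CAC 0.7): r = 0.7 × 1.10/2.09 = 0.368; 2/1.368 = 1.462, about 46%.
- If returning patients push r to 0.8-0.9: 2/1.8 = 1.11 and 2/1.9 = 1.05, i.e. 11% and 5%.

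**4. The plan's rolling windows.** Each monthly row looks back 365 days (section 10.4.1), and section 5.3 gives December 2020 as nine pre-intervention months plus three intervention months. Treating a row as the average of its 12 months (an approximation), the row after k intervention months carries weight w = min(k, 12)/12 on intervention data. If a clinic starts d points above average and there is no effect, its expected excess is d × [1 - (1 - r) × w]. The fade is gradual, so it enters the slope.

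The least-squares slope of w on k over k = 1 to 18 is (341/12)/484.5 = 0.0587 per month. The false slope is therefore -0.0587 × (1 - r) × d: for r = 0.731 to 0.368, -0.016 to -0.037 points per month for each point of baseline imbalance.

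The slope's excess variance without the interaction is 1/(1 - ρ²) - 1, where ρ is the correlation between a clinic's intervention-period slope and its baseline rate. Computed from the covariance of monthly clinic means with the inputs of step 3, ρ² runs from 0.104 to 0.240: 1/0.896 = 1.12 and 1/0.760 = 1.32, or 12% to 32%. A linear simulation of the same setting gave 12% to 33%. For the jump at intervention start, the excess was about 3% or less.

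**The case against.** Several objections have force.

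- **Exact cancellation.** A reader might infer that the covariates drop out of every coefficient. That is exact only in a balanced linear model; this one is logistic, with random effects and six practices with short baselines. In the last-resort model without random effects, which 10.5 provides only for secondary and safety outcomes, they moved arm × period by up to 0.23 log-odds under an assumed panel shift.
- **Reliance.** A reader might infer that the plan counts on these terms to repair the PSA coding error. It does not say so; 10.2 defers to the protocol paper, which is not available here.
- **PSA imbalance.** A reader might infer that PSA baseline was left wholly unconstrained. Eligible count and order count were both constrained, which partly constrains the rate. With clinic-size CV 0.3 (assumed), those two constraints cut the SD of the arm-rate difference in simulation from 1.5-1.8 to 0.6-0.7 points; with CV 0.9, from 1.7-2.3 to 1.3-1.5. No single bias figure for PSA is supported.
- **Power.** A reader might infer a shortfall against Table 1. Table 1 assumes no baseline adjustment. At ICC 0.017 and CAC 0.8, the change-score variance relative to a post-only comparison, 2(1 - r), is 0.83 (PSA), 0.95 (DM) and 0.70 (UA/UC). Whether Table 1 itself reproduces is a separate matter.
- **Independent periods.** The 16-46% range ignores the overlapping look-back windows. This stands.
- **Wrong coefficient.** 10.5 interprets the slope, and step 2 shows no gain there. That result comes from independent months; with rolling windows the gain moves to the slope.
- **Preference.** Difference-in-differences is the declared framework and is unbiased over randomization. True, and this limits the point to precision and conditional bias.

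**Conclusion.** The point holds in limited form. In the co-primary mixed model the randomization variables, as written, contribute essentially nothing, though not exactly nothing, to arm × period and arm × period × time. They do not serve the purpose 10.5 gives them, and change that depends on the baseline rate is left unadjusted.

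The size of the loss rests on an assumed autocorrelation and an ICC of 0.010-0.017. With rolling windows, the setting closest to the plan, the level gain from a working adjustment is near zero and the slope variance without it is roughly 12-33% larger. That range is for an unconstrained baseline rate. UA/UC and DM rates were constrained directly, so chance imbalance there should be small; PSA was constrained in part.

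The documents do not support calling the primary analysis invalid. The arm term and the historical rows already absorb a level difference between arms. The change is worth making because it is cheap and touches the coefficient that the plan interprets.

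**What to change.** In each co-primary model, interact the clinic's own pre-intervention rate of that outcome (centred) with period and with time in the intervention period. Alternatively, model the intervention-period rows only, with that rate and rate × time as covariates; this is similar in aim but will not give identical numbers. State what the remaining randomization variables are for if they stay as main effects. Name the annual PSA overtesting rate, not the number of PSA orders, as the PSA covariate.

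The baseline rate shares months with the early intervention rows. That is acceptable because it was fixed before randomization in June 2020, and the time interaction is what handles the overlap.

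The cost is a few lines of SAP text and one or two extra parameters per model. The rates come from EHR data already abstracted for the randomization. If outcomes by arm have already been seen, report the adjusted model as a labelled sensitivity analysis.
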